2.5 Section 6 Trial Population

6.2 Inclusion criteria:

Age ≥ 12 years and body weight ≥ 35 kg (except for Croatia, ~~and~~ The Netherlands *and France* where the lower age limit will be 18 years)

6.4 Criteria for rescheduling planned visits:

Criteria 3: In a bleeding state (all visits including PK). *If a patient experiences a bleeding episode during a PK session between visit 2a and 2b, PK sampling will be stopped and the patient will receive treatment with N8-GP, (or the patients' previous FVIII product if the bleeding episode occurs at home and requires immediate treatment)^g. In case of mild or moderate bleeding episodes, rescheduling of PK sessions can be done at the discretion of the Investigator taking the patient's safety into account. In case of a severe bleeding episode the PK session must be discontinued.*

Footnote g: A 7 days wash-out is needed before the rescheduled PK session if the bleeding episode was treated with N8-GP and a 4 days wash-out is needed if the bleeding episode was treated with previous FVIII product.

6.5 Withdrawal Criteria:

- Criteria 4: Use of Coagulation Factors FVIII, FIX and FVII-containing products other than N8-GP and other FVIII-containing products like fresh frozen plasma or cryoprecipitate (**Exception:** current FVIII is allowed until 72 hours before visit 2a *and in case of home treatment of a bleeding episode that requires immediate treatment between visit 2a and 2b*)

2.6 Section 8 Methods and Assessments

8.1.2 Visit Schedule for Patients on Prophylaxis not Undergoing PK Evaluation and for Patients on On-Demand Treatment

At visit 2a, the patients will have their first dose of N8-GP (50 U/kg ~~BW~~) administered at the site. The second dose (50 U/kg BW) is given at visit 2b 4 days after visit 2a. If a bleeding occurs during this period the patient must *contact the site and preferably* come to the site for treatment with N8-GP. *If the patient has a bleeding episode that requires immediate treatment or the Investigator judges it as necessary, the patient can treat himself at home with his previous FVIII product.*

After each of the 2 initial doses of N8-GP, patients must be observed for adverse reactions for at least 1hr after dosing.

The samples taken post-dose must not be taken from the same vein as previously used for administration of N8-GP.

Patients will be provided with an eDiary and will be carefully trained in the use of this eDiary including instructions in reporting details of bleeding episodes and prophylactic treatment including doses administered at *all visits after visit 2b*.

8.1.3.1 Visit 2a for Patients on Prophylaxis Undergoing PK Evaluation

.....

At visit 2a the patients will receive their first dose of N8-GP (50 U/kg BW) at the site and 9 PK samples will be taken during the following 4 days. *If a bleeding occurs between visit 2a and 2b the patient must contact the site and preferably come to the site for treatment with N8-GP. If the patient has a bleeding episode that requires immediate treatment or the Investigator judges it as necessary, the patient can treat himself at home with his previous FVIII product.*

.....

Patients will be provided with an eDiary and will be carefully trained in the use of this eDiary including instruction in reporting details of bleeding episodes and prophylactic treatment including doses administered at all visits after visit 2b.

8.1.4 Follow-up visit (only for patients withdrawn due to development of FVIII inhibitors)

.....

Blood sampling for central laboratory assessments:

- FVIII inhibitors, see section 8.3.2.2
- *N8-GP binding antibodies, see section 8.3.2.1*

8.1.5 Unscheduled Visits

...

The following can be performed/reported at an unscheduled visit:

...

- *Check date and time of last coagulation factor administration (see section 8.4.3)*

8.2.1 Bleeding episodes

For bleeding episodes the following will be recorded in Patient's eDiary or eCRF:

.....

- *Date and time for Sstop of bleed (e.g. pain reduction with no increase in swelling) (~~date and time~~)*

A need for haemostatic rescue therapy with another FVIII product will be assessed by the Investigator via phone or during the site visit. Patients treated with FVIII products other than N8-GP must be withdrawn from the trial (*exception: current FVIII is allowed until 72 hours before visit 2a and in case of home treatment of a bleeding episode that requires immediate treatment between visit 2a and 2b*).

8.3.2.2 FVIII inhibitors

...

If the Investigator decides to send a sample for inhibitor testing to a local laboratory, the Investigator must also send a duplicate sample for inhibitor testing to the Central Laboratory. The data from the Central Laboratory will then be used in the official analysis. *Any single A-positive inhibitor test must be reported as a MESI (please refer to section 12.1.2).*

...

A patient having an initial positive inhibitor ~~positive~~ test and a second negative inhibitor test, *will be regarded as inhibitor negative and can ~~will be reported as a MESI and~~ continue in the trial.*

8.3.6.2 Urinalysis

...

Urinalysis will be performed locally with sticks provided by the central laboratory and should be recorded *on the laboratory requisition form ~~directly in the e-CRF~~*. Results from the urinalysis other than pH, proteins, glucose, bilirubin and blood should not be reported to Novo Nordisk.

8.3.7 Central Laboratory Assessments

.....

All blood samples including genotyping blood sample will be destroyed after finalisation of the trial report. Blood samples of patients who are suspected of inhibitors or who have developed inhibitors will be stored at least until evaluation of the clinical trial data by the authorities in the patient's country.

8.3.7.4 Viral Assessments (HIV, Hepatitis B and C):

Viral assessments ~~should~~ *must* be performed if status is unknown *or if known* or the investigator consider there is an indication to test

8.3.7.5 FVIII genotype testing:

At visit 1, all patients/LARs will be asked about documentation of previous FVIII genotype tests. If not available or if it needs to be re-tested FVIII genotype testing will be offered at visit 3~~4~~. Investigator and patients/LARs have the right to refuse to provide patient's FVIII genotype documentation or to refuse genotyping.

8.4.3 eDiaries:

...

- Bleeding episodes

...

- *Date and time* for Sstop of bleed (*e.g. pain reduction with no increase in swelling*)(~~date and time~~)

Trial product administration performed at the site should also be entered in the eDiary by the patient, *except the first two doses of N8-GP administrated at visit 2a and 2b. These will be entered into the eCRF by the site. If the patient have used their previous FVIII product to treat a bleeding episode between visit 2a and 2b, this information will be entered in the eCRF.*

8.4.4.1 Documentation of Inhibitor Status

A positive inhibitor test excludes the patient. The historical laboratory cut-off value (assay sensitivity or lower limit of quantification) for a positive Bethesda inhibitor titre must not be higher than 1.0 BU/mL.

Documentation of inhibitor status must include the following:

- two inhibitor test result should be documented within the period since diagnosis, *not necessary within the last 8 years*
- FVIII recovery test + *evaluation of the bleeding history AND/OR negative inhibitor testing* performed at least every third year during the last 8 years ~~+ evaluation of the bleeding history AND/OR negative inhibitor testing at least every third year during the last 8 years.~~

2.7 Section 11 Concomitant Illness and Concomitant Medication

Coagulation Factors: FVIII, FIX and FVII-containing products other than N8-GP and other FVIII-containing products like fresh frozen plasma or cryoprecipitate (exception: current FVIII is allowed until 72 hours before visit 2a *and in case of home treatment of a bleeding episode that requires immediate treatment between visit 2a and 2b*)

2.8 Section 12 Adverse Events and Pregnancies

12 Adverse Events, *Technical Complaints* and Pregnancies

12.1.2 Medical event of Special interest

...

A MESI should *be* reported following the same reporting requirements and timelines for SAEs (see section 12.2) irrespective of if the MESI fulfils an SAE criterion.

The following events are defined as MESIs in this trial;

1. Medication error

- Administration of wrong drug or *use of wrong device*
- wrong route of administration such as intramuscular instead of intravenous
- Administration of an accidental overdose, ie dose which may lead to significant health consequence as judged by the investigator irrespective of whether a SAE criterion is met.
- Administration of a high dose with the intention to cause harm *e.g. suicide attempt*

2. Inhibitor formation against FVIII

- Blood samples for measurement of FVIII inhibitors will be analysed at the central laboratory selected by Novo Nordisk and if positive ($BU \geq 0.6/mL$) should be reported as a MESI. *A patient is only considered to be inhibitor positive ($BU \geq 0.6/mL$) if the inhibitor test is positive at two consecutive tests - sampled preferably within 2 weeks.*

...

MESIs are reported by completing an AE form and safety information form. Complete the AE form in the eCRF. If for any reason the EDC application is unavailable, then fax, telephone or email Novo Nordisk. Complete the safety information forms on paper CRFs.

12.2 Collection, Recording and Reporting of Adverse Events

All events meeting the definition of an AE must be collected and reported ~~for all medicinal products.~~

12.2.1 Follow up of Adverse Events:

...

Non-serious AEs must be followed until outcome of the event is “recovering”, “recovered” or “recovered with sequelae” or until the end of the follow-up period stated in the protocol, whichever comes first, and until all queries related to these AEs have been resolved. Cases of chronic conditions or cancer or AEs ongoing at time of death (where death is due to another AE) may be closed with an outcome of “recovering” or “not recovered” ~~All non-serious AEs classified as severe or possibly/probably related to the trial product must be followed until the subject has “recovered” or “recovered with sequelae”, and all queries have been resolved. Cases of chronic conditions or cancer or AEs ongoing at time of death (i.e. subject dies from another AE) can be closed with an outcome of “recovering” or “not recovered”. Cases can be closed with an outcome of “recovering” when the subject has completed the post-trial follow-up period and is expected by the Investigator to recover.~~

~~All other non-serious AEs must be followed until the outcome of the event is “recovering”, “recovered” or “recovered with sequelae” or until the end of the post-treatment follow-up stated in the protocol, whichever comes first, and until all queries related to these AEs have been resolved. AEs ongoing at time of death (i.e. subject dies from another AE) can be closed with an outcome of “recovering” or “not recovered”.~~

12.3.2 Collection, Storage and Shipment of Technical Complaint Samples

...

The **technical complaint sample** and a **paper copy of the technical complaint form** must be sent to Novo Nordisk within **5 calendar days** of receiving the technical complaint sample at trial site by using the following address:

- Novo Nordisk A/S,
Att.: Customer Complaint Center,
[name],
[name],
Denmark

2.9 Section 18 Statistical Considerations

18.1 Sample Size Calculations

Co-Primary Endpoint: Incidence Rate of *FVIII*-inhibitors ~~Inhibitory Antibodies against *FVIII*~~ Defined as ~~Titre~~ ≥ 0.6 BU/mL

Given the rarity of the disease, a sample size of 105 patients treated for a minimum of 50 exposure days will allow for a reasonable evaluation of inhibitor formation in this pivotal trial.

The aim is to demonstrate that the upper confidence limit for the inhibitor rate is below 6.8%. In practical terms this will happen if 2 or less inhibitors are observed in the planned 105 patients with 50 exposure days (3 or less if the trial should end with 127 patients with 50 EDs). If the true inhibitor rate of N8-GP is 0,5 ±% then the chance/power to achieve a maximum of 2 inhibitors out of 132 patients entered into the trial will be ~~85%~~ 97%.

Co-Primary Endpoint: Annualised bleeding rate in the prophylaxis arm

The clinical efficacy of N8-GP in long term bleeding prophylaxis will be evaluated based on all the prophylaxis period data. This will give different period lengths for the different patients but on average it is expected to give about 12 month prophylaxis treatment per patient (~7 months for the last recruited patients and ~17-19 months for the first recruited patients). Prophylactic effect will be concluded if the upper 97.5% confidence limit for the annualised bleeding frequency is < 8.5.

Annualised bleeding rate for withdrawals will be imputed for the missing period based on their observed bleeding rate except for patients withdrawn within one month where imputation will be performed based on an annualised bleeding rate of 24. The true bleeding rate will be assumed to be 6.8 as for historical prophylaxis data but for the sample size calculation it will be assumed that 1 patient will withdraw within 1 month and that will lift the effective annualised bleeding rate for the power calculation by $24/120 = 0.2$, i.e. from 6.8 to 7.0.

The model will be a Poisson regression allowing for over-dispersion (using Pearson's chi-square divided by the degrees of freedom (i.e. Scale=Pearson in SAS)) and using log observation time as offset to account for the differing treatment lengths. Based on an approximation to the normal distribution and assuming that the patients bleed 7.0 ~~6.8~~ times per year and an over-dispersion of 5 (so variance ~~34~~ 35) 120 patients entered on prophylaxis will give a power of ~~89%~~ 79%.

The power calculation is sensitive to the assumed over-dispersion (OD) of 5. For this reason, an interim analysis will be performed to evaluate the OD when approximately 90 patients have been recruited to prophylaxis: If the estimated OD for the full study is larger than 6, then the sample size will be adjusted up to 160 on prophylaxis to ensure that the power holds. The sample size will not be increased without issuing a protocol amendment.

The following table shows the power for the various assumptions of bleeding rates and over-dispersions (OD).

True ABR	OD	Power for the Prophylaxis test power
7.0 6.8	5	79% 89%
6.8 6.5	5	89% 97%
6.5 6	5	97% 99,9%
7.0 6,8	4	87% 83%
7.0 6,8	6	72% 95%

Combined *p*Power

With 97% power for the first co-primary endpoint and 79% power for the second co-primary endpoint, the combined power for the study with the given sample size is expected to be about $97\% * 79\% = 76\%$

~~With 85% power for the first co-primary endpoint and 89% power for the second co-primary endpoint the combined power for the study with the given sample size is expected to be about $85\% * 89\% = 76\%$.~~

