Approximately 150 (190)¹ (see section 18.5) patients are planned to be screened in order to dose approximately 132 (172)¹ (see section 18.5) patients in the trial out of which 105 (145)¹ (see section 18.5) patients are expected to complete the prophylaxis part of the trial and a minimum of 10 patients are expected to complete approximately 6 months in the on-demand part of the trial.

Section 6.1 Number of Patients to be Studied

Countries planned to participate: Australia, Brazil, Croatia, Denmark, France, Germany, Hungary, Israel, Italy, Japan, Korea, Malaysia, Netherlands, Norway, Russia, Spain, Sweden, Switzerland, Taiwan, Turkey, United Kingdom and United States

Planned number of patients to be screened (i.e. documented informed consent) approximately: 150 (190)¹ (see section 18.5)

Planned number of patients to be started on trial product(s) approximately: 132 (172)¹ (see section 18.5)

Planned number of patients to complete the trial *approximately*: ≥ 115 (155) (see section 18.5)

- Minimum 15 patients must be 12-17 years old at screening
- Minimum 10 patients must be in the on-demand arm
- ~~Minimum~~ *Approximately 105 (145)¹ (see section 18.5)* patients must be in the prophylaxis arm

Planned number of trial sites (approximately): 75

Section 6.6 Patient Replacement

Patients withdrawn from the trial can be replaced until *approximately* 105 (145)¹ (see section 18.5) patients in the prophylaxis arm have had at least 50 EDs, and 10 patients have had 20 bleeding episodes in the on-demand and/or the prophylaxis arm.

Section 7 Trial Schedule

Planned duration of recruitment period: 12 (14)¹ months

.....

Planned date for LPLV: 01-Oct (Dec) (See section 18.5)--2013

Section 18.1 Sample Size Calculation

Co-Primary Endpoint: Annualised bleeding rate in the prophylaxis arm

.....

The power calculation is sensitive to the assumed over-dispersion (OD) of 5. For this reason an interim analysis will be performed to evaluate the OD when approximately 90 patients have been recruited to prophylaxis: If the estimated OD for the full study is larger than 6, then the sample size will be adjusted up to 160 on prophylaxis and in that way ensure that the power holds. ~~The sample size will not be increased without issuing a protocol amendment.~~

Section 18.5 Interim Analysis

.....

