18.1 Sample Size Calculation

The study has two co-primary endpoints *for the Main Phase* that both need to succeed for the study to succeed. The two endpoints can reasonably be considered approximately independent and combined power then becomes the product of the individual power for each co-primary endpoint.

.....

Co-Primary Endpoint: Annualised bleeding rate in the prophylaxis arm

The clinical efficacy of N8-GP in long term bleeding prophylaxis will be evaluated based on all the prophylaxis period data. This will give different period lengths for the different patients but on average it is expected to give about 12 month prophylaxis treatment per patient (~7 months for the last recruited patients and *approximately 17–19 months* for the first recruited patients).

Prophylactic effect will be concluded if the upper 97.5% confidence limit for the annualised bleeding frequency is < 8.5. Annualised bleeding rate for withdrawals will be imputed for the missing period based on their observed bleeding rate except for patients withdrawn within one month where imputation will be performed based on an annualised bleeding rate of 24. The true bleeding rate will be assumed to be 6.8 as for historical prophylaxis data but for the sample size calculation it will further be assumed that 1 patient will withdraw within 1 month and that will lift the effective annualised bleeding rate for the power calculation by $24/120 = 0.2$, i.e. from 6.8 to 7.0.

.....

Operationally the null-hypothesis will be rejected and a success rate acceptably close to 80% is considered confirmed if the lower bound of the 1-sided 97.5% confidence interval for the rate is above 65%. By assuming that the observations are independent, the power may be calculated exact using the binomial distribution. The power will depend on the number of bleeding episodes actually observed. It is expected that more than 200 bleeding episodes will occur in the *Main Phase of the trial* in the on-demand arm and the prophylaxis arms combined. Assuming a true response rate of 80% the power for this endpoint is greater than 95%. Correlation between observations corresponding to the same patient may reduce this power but is not expected to affect it too much.

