18.2 Statistical Methods

18.2.1 General Considerations

Novo Nordisk A/S will be responsible for the statistical analysis. All tests will be performed as 1-sided tests on 2.5% significance level.

All bleeding endpoints will be evaluated based on bleeding episodes requiring treatment with N8-GP. Non-treatment requiring bleeding episodes that coincide with regular prophylaxis doses are not included.

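### The stated 79% ABR power and 76% combined power come from a rate-scale formula; the planned log-link Poisson test delivers about 71–73% and about 70%

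*Protocol*

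**What the plan says.** Amendment 6, section 18.1, sets the decision rule for the ABR co-primary endpoint: "Prophylactic effect will be concluded if the upper 97.5% confidence limit for the annualised bleeding frequency is < 8.5". The model there is a Poisson regression with Pearson over-dispersion, "using log observation time as offset to account for the differing treatment lengths". SAP section 2.2.2 specifies the same model with a log-duration offset. Tests are one-sided at 2.5% (Amendment 13, section 18.2.1).

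Power is described as a normal approximation for 120 patients with an ABR of 7.0 and a variance of 35 (over-dispersion 5), giving 79%. A five-row table covers other rates and over-dispersions. The combined statement reads "With 97% power for the first co-primary endpoint and 79% power for the second co-primary endpoint, the combined power for the study", followed by 97% × 79% = 76%.

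The ABR of 7.0 is the historical 6.8 plus an allowance for one early withdrawal imputed at 24 bleeds per year, said to "lift the effective annualised bleeding rate for the power calculation by" 24/120 = 0.2.

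The protocol also says "The power calculation is sensitive to the assumed over-dispersion (OD) of 5". If the projected over-dispersion exceeds 6, "then the sample size will be adjusted up to 160 on prophylaxis and in that way ensure that the power holds" (Amendment 10, section 18.1). Neither Amendment 10 nor Amendment 13 changes the 79% or the 76%, and SAP section 2.1 refers back to protocol section 18.1 for sample size.

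**The concern.** A log-time offset makes the model linear in the log rate. Its Wald upper limit is therefore exp(log rate + 1.96 × SE), which lies further above the estimate than a symmetric limit on the rate would. The upper side is the one the test uses. A power formula built from the variance of the rate describes a different, easier test.

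Both co-primary endpoints must succeed, so an overstated ABR power feeds directly into the trial's overall power. The same section presents the increase to 160 patients as preserving power, and that assurance has no stated upper limit on over-dispersion. The uplift of 0.2 also looks wrong: it adds the full 24 for a patient who already counts at 6.8.

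**Working it through.** **Inputs.** Margin 8.5, one-sided 2.5% (z = 1.96), N = 120, ABR 7.0, over-dispersion (OD) 5, mean follow-up about 1 year. All are from Amendment 6, section 18.1, except the test level (section 18.2.1).

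**1. Reproduce the stated figure (rate scale).** Power = Φ((8.5 − r)/√(r × OD/N) − 1.96).

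For r = 7.0 and OD 5: √(35/120) = 0.540; 1.5/0.540 = 2.78; Φ(0.82) = 79.3%. The formula matches all five rows of the table. Using the variance under the null gives 73.2%, which does not match.

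**2. Power of the planned test (log scale).** Power = Φ(ln(8.5/r)/√(OD/(r × N)) − 1.96).

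For r = 7.0 and OD 5: ln(8.5/7.0) = 0.194; √(5/840) = 0.0772; ratio 2.52; Φ(0.56) = 71.1%. Taking the standard error at the observed rate gives 72.6–73.1%.

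**3. Simulation of the test.** Gamma-Poisson counts with k = r/(OD − 1), intercept-only Poisson fit, Pearson scale, success if the log-Wald upper limit is below 8.5. Base case: 72.3% with one year per patient (200,000 trials); 72.4% with follow-up uniform over 7–18 months.

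| ABR | OD | Stated | Rate-scale formula | Log-scale formula | Simulation |
|---|---|---|---|---|---|
| 7.0 | 5 | 79% | 79.3% | 71.1% | 72.3% |
| 6.8 | 5 | 89% | 89.1% | 81.4% | 82.6% |
| 6.5 | 5 | 97% | 97.0% | 91.8% | 92.9% |
| 7.0 | 4 | 87% | 87.4% | 80.3% | 81.7% |
| 7.0 | 6 | 72% | 71.8% | 63.2% | 64.6% |

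**4. Combined power.** The inhibitor figure is right: P(at most 2 of 132 at a true rate of 0.5%) = 97.1%. With the product rule, 0.97 × 0.711 = 69.0% and 0.97 × 0.731 = 70.9%, against the stated 76%.

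**5. The uplift.** The early withdrawal is one of the 120 and already carries 6.8, so the lift is (24 − 6.8)/120 = 17.2/120 = 0.14, giving an ABR of 6.94. The log-scale formula then gives 74%. Simulating the scenario literally (119 patients at 6.8, one fixed at 24) gives 74.9%. Combined: 0.97 × 0.74 to 0.97 × 0.75, or 72–73%.

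**6. The increase to 160.** In both formulas, power at a given ABR depends on OD and N only through OD/N. So 160 patients restore the 120-patient, OD 5 power only while OD ≤ 5 × 160/120 = 6.67. At ABR 7.0 and N = 160:

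- OD 6: 83.3% on the rate scale, 75.6% on the log scale.
- OD 8 (chosen here as an illustration): 72% on the rate scale, 63% on the log scale.

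**The case against.** The protocol discloses a normal approximation and calls the combined figure approximate, and its arithmetic is right for the method it used. That is fair: the error lies in the choice of scale. But the scale is not disclosed, and the 8-point gap at the base case exceeds the 7 points the table itself shows between OD 5 and OD 6.

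The log scale does not explain the whole gap. In simulation, a symmetric rate-scale limit with estimated standard error reaches 76.7%, so about 4.4 points (76.7 − 72.3) are due to scale and the rest to the closed-form approximation. This stands as a refinement, but the 79% is not reached at ABR 7.0 on either scale.

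The documents do not name the interval type. A likelihood-ratio limit from the same model gives about 74% at ABR 7.0 and about 76% in the literal 119-plus-one scenario. That narrows the gap without closing it.

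The sample-size trigger is defined on over-dispersion alone. No power threshold enters it, and the scale of the power formula does not move it. This is correct. What remains is the promise attached to the trigger. At OD 6, 160 patients do better than 120 at OD 5 (75.6% against 71.1%), so power holds at the trigger point. It fails above about 6.7, on either scale, and the rule sets no ceiling.

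Finally, SAP section 2 records that the pivotal part has been reported, so no analysis changes. True, but SAP section 2.1 still sends readers to section 18.1 for the power.

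**Conclusion.** The concern holds. At the protocol's own inputs the planned test has about 71–73% power for ABR, not 79%, and combined power is about 70%, not 76%. All five table rows are overstated, by about 4 to 9 points. With the uplift corrected to 0.14, which works in the sponsor's favour, the figures are 74–75% and 72–73%, still below those stated. The assurance about 160 patients is valid only up to an OD of about 6.7.

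These results assume a Wald limit on the log scale, which follows from the log offset although the link is not named. They also assume gamma-Poisson over-dispersion in the simulations and about one year of mean follow-up. The issue concerns planning power only. It does not bear on the decision rule or the validity of the test.

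**What to change.** In protocol section 18.1:

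- Restate the ABR power on the log scale and the combined power with it. If ABR 7.0 is kept, these are about 71–73% and about 70%. If the uplift is corrected to (24 − 6.8)/120 = 0.14, they are 74–75% and 72–73%. The second pair is preferable because it corrects both points; whichever is used, state the input rate beside it.
- Recompute all five table rows with Φ(ln(8.5/r)/√(OD/(r × N)) − 1.96), and name the scale.
- Replace the claim that 160 patients ensure the power with the OD up to which they do so (about 6.7), and give the power above it.

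The cost is protocol wording and a slightly less favourable stated power. Enrolment, the model, the 8.5 criterion and the over-dispersion trigger stay as they are.
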